15.3. Missing Efficacy Data

ADSD and ANSD

Global score to be calculated if both conditions meet

- There are at least 4 items (out of 6) available at each day.
- There are at least 4 days available to calculate the average weekly score. For post baseline visits, if less than 4 measurements are available from the 7 days prior the visit [including the day of the visit for ANSD], the most recent 4 measurements from the 11 days prior the visit will be used for the calculation; if finally, less than 4 measurements are available, it will be considered as missing.

- A given score cannot be calculated if there is at least one response used for the calculation that is missing.
- Responses from other assessments should not be used to impute missing data. For example, if a participant indicated that he worked 40 hours at one assessment, but left that question blank on another assessment, the blank response should remain missing.
- If the participant entered a range of hours, the midpoint should be considered for the analysis.

Asthma Control Questionnaire (and ACQ-5)

- Based on the manual of ACQ (2), any more than one missing value is not acceptable. If more than one of the questions have missing value, the global score is invalid and will be considered as missing. If only one question has missing score, it will be interpolated (pro-rated) using the completed questionnaires from the previous visit. For instance, answer to question 5 is missing at Visit 4, and all questions are completed at Visit 3. Then the question 5 score at Visit 4 is interpolated as: $(\text{sum of score at Visit 4} / \text{sum of scores excluding question 5 at Visit 3}) \times \text{score of question 5 at Visit 3}$. If the questionnaire from the previous visit is not complete either, the missing value will be imputed as the average of the completed questions within the current visit.

- To have a valid overall score, it is not acceptable to have more than three missing responses or more than one missing response per domain. For responses with more than acceptable amount of missing value(s), the overall score will be considered as missing. For responses with amount of missing value(s) within accept range, the missing score will be interpolated using the previous completions of the questionnaire following the similar algorithm used for ACQ.

Other Participant-Reported Outcomes

For all other questionnaires, if one or more questions are left unanswered, the questionnaire is not scored.

No imputation will be made for the missing values.

15.4. Missing Safety Data

For categorical variables, participants with missing data are not included in calculations of percentages unless otherwise specified. When relevant, the number of participants with missing data is presented.

15.4.1. Handling of missing age

If age is missing but year of birth is collected, then age will be derived as year of informed consent signed minus year of birth.

15.4.2. Handling of computation of study intervention duration if investigational medicinal product end of treatment date is missing

For the calculation of the study intervention duration, the date of the last dose of IMP is equal to the date of last administration reported on the eCRF “Treatment status” page. If this date is missing, the last available administration date in the “Exposure” form will be used.

The last dose intake should be clearly identified in the eCRF and should not be approximated by the last returned package date.

15.4.3. Handling of medication missing/partial dates

No imputation of medication start/end dates or times will be performed. If a medication date or time is missing or partially missing and it cannot be determined whether it was taken prior or concomitantly, it will be considered a prior, concomitant, and post-treatment medication.

15.4.4. Handling of adverse events with missing or partial date/time of onset

Missing or partial adverse event onset dates and times will be imputed so that if the partial adverse event onset date/time information does not indicate that the adverse event started prior to treatment or after the treatment period, the adverse event will be classified as treatment-emergent. No imputation of adverse event end dates/times will be performed. These data imputations are for categorization purpose only and will not be used in listings. No imputation is planned for date/time of adverse event resolution.

15.4.5. Handling of adverse events when date and time of first investigational medicinal product administration is missing

When the date and time of the first IMP administration is missing, all adverse events that occurred on or after the day of randomization should be considered as treatment-emergent adverse events. The exposure duration should be kept as missing.

The last dose intake should be clearly identified in the eCRF and should not be approximated by the last returned package date.

15.4.6. Handling of missing assessment of relationship of adverse events to investigational medicinal product

If the assessment of the relationship to IMP is missing, then the relationship to IMP has to be assumed and the adverse event considered as such in the frequency tables of related adverse events, but no imputation should be done at the data level.

15.4.7. Handling of missing severity/grades of adverse events

If the severity/grade is missing for 1 of the treatment-emergent occurrences of an adverse event, the maximal severity on the remaining occurrences will be considered. If the severity is missing for all the occurrences, a “missing” category will be added in the summary table.

15.4.8. Handling of potentially clinically significant abnormalities

For PCSAs with 2 conditions, one based on a change from baseline value or a normal range and the other on a threshold value, with the first condition being missing, the PCSA will be based only on the second condition.

15.5. Visit Windows

The analysis window below “[in brackets]” will be applied to post-baseline measurements to allocate them to a scheduled visit for the parameter (see [Appendix 15.2](#) for details of scheduled visits).

Table 15-1 Analyses window definition

Scheduled visit post baseline	Targeted study day* **	■/Weight/ Eosinophil parameters	■ parameter	Diary data (Asthma sleep disturbance questionnaire/ Sleep diary)	All other parameters
Week 4 (Visit 3)	29		[2, 56]	[2, 29]	[2, 42]
Week 8 (Visit 4)	57			[30, 57]	[43, 70]
Week 12 (Visit 5)	85	[2, ∞]	[57, ∞]	[58, ∞]	[71, ∞]

* The reference day (denoted as Day 1) for the calculation of study day will be the day of the first administration of IMP (except for participants randomized but not exposed). (See [Section 4.4.6](#)).

** For actigraphy data as well as for ADSD/ANSD parameters, each post-baseline assessment will be allocated to a scheduled visit, taking into account **the day of the corresponding actual visit on site**. For other parameters (daily collected or collected once per visit) each post-baseline assessment will be allocated to a scheduled visit, taking into account **the day of the assessment**.

After applying the above time windows, if multiple assessments are associated to the same time point, the closest from the targeted study day will be used. In case of equality, the last measurement will be used. Re-allocated scheduled visits (i.e., visit numbers) should be sequential if ordered by the date of measurement.

If there is no measurement available for a given parameter in an analysis window data, is considered missing for the corresponding visit.

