Home dosing diary k			X	X	X	X	X	Paper diary
Asthma background therapy diary k			X	X	X	X	X	Paper diary
	X l		X	X	X	X	X	■ should be conducted prior to spirometry and the participant should refrain from eating and drinking for ≥1 hour before the procedure.
Spirometry m	X m		X	X	X	X	X	
Reversibility test	X n							Only required if a reversibility test meeting eligibility criterion was not performed within 6 months prior to SV1

- a Science37 Metasite: all the study procedures will be done at participant's home by Science37 using telemedicine (TM), mobile study nurses, and an electronic application called the Science37 Platform. As part of this study, Science37 participants will see their study doctors by using a TM model during the study.
- b In exceptional situations when the participant cannot attend an on-site visit during the intervention period, the visit can be performed remotely ensuring at least the procedures that can be done at home: PROs completion, actigraphy, home [REDACTED] if applicable, IMP administration, blood samples collection, pregnancy test, if applicable, safety reporting, and concomitant medications.
- c **Post-treatment Follow-up:** up to 12 weeks or until the participant switches to commercialized dupilumab (or other biologic product), whatever comes first.
- d **ETD:** Participants who prematurely discontinue the study intervention (prior to completing the 12-week treatment period) should attend an ETD visit at earliest convenience with all the assessments planned for the EOT visit (Visit 5), except IMP. In particular cases when the ETD visit is close to a regular study visit, ETD could be merged and will replace the regular visit. In addition, the participants will be asked and encouraged to complete all the remaining study visits according to the visit schedule until and including the EOT visit (Visit 5). Under exceptional circumstances when a participant cannot come to the site for the scheduled visit, a phone contact can be made after sponsor approval is given. During the phone contact, at least information about AEs and concomitant medications should be collected.

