- e **ESD:** Participants who prematurely discontinue the study during the intervention period should attend an ESD visit at earliest convenience with all the procedures planned for the EOT Visit (Visit 5) except IMP. Under exceptional circumstances when a participant cannot come to the site for the scheduled visit, a phone contact can be made after sponsor approval is given. During the phone contact, at least information about AEs and, concomitant medications should be collected.
- f If preferred by the participant and the investigator for logistic reasons, screening visit 1 (SV1) and screening visit 2 (SV2) can be merged into a single on-site visit. Importantly, this single screening visit will have to be done on Day -11 at the latest.

- g Serum pregnancy test at screening visit (SV1) and urine pregnancy tests at the other visits using dipstick. A WOCBP must have a negative highly sensitive pregnancy test at SV1 (serum pregnancy test) and on Day 1 before the first dose of study intervention (urine or serum, if required by local regulations). If a urine test on Day 1 cannot be confirmed as negative (eg, an ambiguous result), a serum pregnancy test is required. In such cases, the participant must be excluded from participation if the serum pregnancy result is positive. In case of positive urinary test during the study, a serum pregnancy test should be performed as soon as possible to confirm the pregnancy. A urine pregnancy test will be performed at home at the follow-up visit.
- h Hepatitis screening covering hepatitis B surface antigen (HBs Ag), total hepatitis B core antibody (total HBcAb); hepatitis C virus antibodies (HCVAb). In case of results showing HBsAg (negative) and HBcAb (positive), HBV DNA testing will be performed to rule out a false positivity or to clarify the serological status if the Investigator finds it unclear to interpret in absence of known HBV infection. In case of results showing HCVAb (positive), HCV RNA testing may be performed to rule out a false positivity. Human Immunodeficiency Virus screening (Anti-HIV-1 and HIV-2 antibodies). Tuberculosis testing will be performed only on a country by country basis according to the routine clinical practice and the local guidelines if required by Regulatory Authorities or Ethics Committees.

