An important potential risk for dupilumab is "eosinophilia associated with clinical symptoms in asthma patients". The observed increase in eosinophil count is transient, which is consistent with the current understanding of the mechanism of action of dupilumab. In dupilumab asthma studies, a small number of patients with asthma experienced serious systemic eosinophilia presenting with clinical features of eosinophilic pneumonia or vasculitis consistent with eosinophilic granulomatosis with polyangiitis, conditions which are often treated with systemic corticosteroid therapy. These events have been seen in other drug development programs for severe asthma and usually, but not always, have been associated with the reduction of OCS therapy suggesting possible unmasking of these conditions with tapering of corticosteroids during dupilumab therapy. The association of dupilumab treatment and these events has not been established. Health care providers should be alert to eosinophilia associated with vasculitic rash, worsening of pulmonary symptoms, pulmonary infiltrate, cardiac complications, and/or neuropathy presenting in their patients, especially upon reduction of systemic corticosteroids.

Patients with known helminth infections were excluded from participation in clinical studies, therefore it is not known if dupilumab will influence the immune response against helminth infections. Consequently, patients with pre-existing helminth infections should be treated for their helminth infection before initiating therapy with dupilumab.

Other potential risks based on the safety profile in particular indications are discussed in the IB. It is anticipated that dupilumab in patients with uncontrolled persistent asthma will have a favorable safety profile as observed across other Type 2-driven immunological disorders.

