4.4.4. Unscheduled Visits

Unscheduled visit measurements will be used in the analysis on efficacy variables and will be included in the by-visit summaries for the safety variables if they are re-allocated to scheduled visits according to the visit window definitions in [section 15.5](#).

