9.2. Clinical Laboratory Evaluations

The laboratory tests will be performed by the local laboratories according to routine clinical practice at site and country level. The Investigator will review the laboratory report, document this review, and record any clinically relevant findings/changes occurring during the study in the AE section of the CRF.

The following laboratory tests will be performed:

- Hematology: blood eosinophil count
- Highly sensitive (serum at screening and urine at the other visits) human chorionic gonadotropin (hCG) pregnancy test (as needed for women of childbearing potential).
- Hepatitis screening covering hepatitis B surface antigen (HBsAg), total hepatitis B core antibody (total HBcAb); hepatitis C virus antibodies (HCVAb).
- Human Immunodeficiency Virus screening (Anti-HIV-1 and HIV-2 antibodies).
- Tuberculosis test performed only on a country by country basis according to the routine clinical practice and the local guidelines or if required by Regulatory Authorities or Ethics Committees.

Additional laboratory tests may be performed at any time during the study as determined necessary by the Investigator or required by local regulations; any clinically significant abnormal lab values will be included in the adverse event analyses. These additional laboratory tests will be displayed in a separate listing.

Eosinophil counts will be summarized for the safety analysis set by study intervention group using descriptive statistics of actual values and change from baseline for each visit or study assessment (baseline and week 12).

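### A participant's early eosinophil count is tabulated as a Week 12 result when there is no Visit 5 sample, because SAP Table 15-1 opens that window at Day 2

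*SAP*

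**What the plan says.** SAP 15.5 states that the windows in Table 15-1 "will be applied to post-baseline measurements to allocate them to a scheduled visit for the parameter". Eosinophils share a column with weight and one redacted parameter. That column has no Week 4 or Week 8 entry, and its Week 12 entry is [2, ∞] with target Day 85. In the column for remaining parameters, Week 12 is [71, ∞]. Three further rules matter:

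- If several values fall in one window, "the closest from the targeted study day will be used".
- The visit counts as missing only in the case "If there is no measurement available for a given parameter in an analysis window".
- Under SAP 4.4.4, unscheduled values are used "if they are re-allocated to scheduled visits according to the visit window definitions".

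After baseline, the schedule of activities (Protocol 1.3) plans eosinophil counts only at Visit 5 and at early discontinuation. A participant who leaves the study "should attend an ESD visit at earliest convenience with all the procedures planned for the EOT Visit (Visit 5) except IMP". One who only stops treatment also has an early-discontinuation visit, but is "asked and encouraged to complete all the remaining study visits according to the visit schedule".

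SAP 9.2 summarizes actual counts and changes from baseline "for each visit or study assessment (baseline and week 12"). Protocol 2.3.1 says of the marker: "The observed increase in eosinophil count is transient". The SAP addendum leaves this window unchanged.

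**The concern.** A row labelled Week 12 should describe participants at about 12 weeks. With a window opening on Day 2, it can include counts taken at two or four weeks from people who left. That would matter little for a stable measurement. Here the protocol itself says the rise comes and goes, so an early count and a Week 12 count are not interchangeable. The SAP 9.2 table is the only post-baseline summary of eosinophil counts visible in the public text, and it would mix the two without saying so.

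**Working it through.** The window is a rule rather than a calculated figure, so the check is to apply it as written: keep values on or after the window's first day, take the one closest to Day 85, and take the later one if tied. Visit 5 is planned at Week 12 ±3 days, that is Days 82 to 88.

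| Post-baseline counts available | Week 12 value under [2, ∞] (as written) | Week 12 value under [71, ∞] |
|---|---|---|
| Day 15 only (early exit) | Day 15 | missing |
| Day 30 only (early exit) | Day 30 | missing |
| Day 40 only (unscheduled) | Day 40 | missing |
| Day 70 only (early exit) | Day 70 | missing |
| Day 71 only (early exit) | Day 71 | Day 71 |
| Day 30 and Day 85 | Day 85 | Day 85 |
| Day 30 and Day 88 | Day 88 | Day 88 |
| Day 40 and Day 84 | Day 84 | Day 84 |

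In the seventh row, for example, the distances from target are |30 − 85| = 55 and |88 − 85| = 3, so Day 88 is taken. The two windows differ only where the last count falls before Day 71.

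**How many could be affected.** The inputs are in SAP 4.1: 260 randomized and 10% dropout. The plan's own figure reproduces: 260 × (1 − 0.10) = 234 evaluable. The ceiling assumes that every dropout leaves before Day 71, gives a sample and has no Visit 5 value: 0.10 × 260 = 26, or 13 per arm if split equally. If dropout were 5% or 15% (my assumption), the ceiling would be 13 or 39. At the cap of 520 participants and 10% dropout it would be 52.

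**How far the summary could move.** Shift in the Week 12 mean = p × d. Here p is the share of early counts in the row, and d is the mean gap between those counts and what the same people would have had at Week 12. At the ceiling p = 26/260 = 0.10. The documents give no value for d. For an assumed gap of 100 to 500 cells/µL in either direction, the shift would be 0.10 × 100 = 10 to 0.10 × 500 = 50 cells/µL. This only shows the scale. Protocol 2.3.1 gives neither the height nor the timing of the rise, so the sign is open too: early counts could precede the rise or fall within it.

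**Whether early counts have another home.** SAP 4.4.6 defines a last on-treatment value for safety parameters as the final measurement in the treatment-emergent period, unscheduled visits included. Addendum item 12 runs that period to 98 days after the last dose, so a count at an early-exit visit would normally fall inside it. SAP 9.3 and 9.4 give weight this row. SAP 9.2 does not give it to eosinophils.

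**The case against.** The strongest reply is that the window is deliberate. Every column of Table 15-1 divides post-baseline time among that parameter's own planned visits: three visits give [2, 42], [43, 70] and [71, ∞]; two give [2, 56] and [57, ∞]; one gives [2, ∞]. Eosinophils have one planned post-baseline visit, and using every available safety value is defensible. This stands as an account of intent. It does not rescue the label: a value that may come from any day after Day 1 is a last or end-of-treatment value, and the SAP reports it as Week 12.

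Several stronger readings are tempting, but the documents do not support them.

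- *Every count from Day 2 becomes a Week 12 result.* It does not; the closest-to-Day-85 rule sets early counts aside whenever a Visit 5 count exists.
- *About 21 participants (8%) will be affected.* This comes from spreading 26 dropouts evenly over Days 2 to 85: 69/84 = 0.82, and 0.82 × 26 ≈ 21. No such spread is stated. The 10% is an allowance for evaluable participants, not a count of people leaving with a blood sample. Protocol 7.2 expects withdrawal to be uncommon, and people lost to follow-up or reached only by phone may give no count.
- *The arm that loses more people early is distorted most.* No difference in dropout between arms is stated anywhere.
- *Monitoring of the eosinophilia risk is weakened.* The important potential risk in Protocol 2.3.1 is eosinophilia with clinical symptoms. It is assessed as an adverse event of special interest by coded search and blinded medical review, which do not use these windows.
- *Weight is equally exposed.* Weight already has a last on-treatment row, its abnormality summary uses all values in the treatment-emergent period, and the statement about transience does not concern it.
- *No other eosinophil summary exists.* The exploratory endpoints are redacted, so this cannot be established.

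**Conclusion.** The point holds as a minor labelling fault. An eosinophil count from an early-discontinuation or unscheduled visit before Day 71 is reported as Week 12 when the participant has no later count. That includes people who stop treatment and then miss Visit 5.

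At the planned size and dropout the ceiling is 26 of 260, on the assumption that all dropouts leave before Day 71 with a sample and no Visit 5 value. The true number is unknown and probably lower. The size and direction of any shift in the Week 12 summary cannot be derived from the documents.

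The effect is confined to descriptive safety output. The primary analysis, alpha, power, adverse events of special interest and the abnormality criteria are unaffected.

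**What to change.** For eosinophils, change the Week 12 window in Table 15-1 from [2, ∞] to [71, ∞], matching the general column. Add the last on-treatment row defined in SAP 4.4.6 to the eosinophil summary in SAP 9.2, so that early counts remain visible under a correct name. Weight already has that row; give its Week 12 window the same bound for consistency. The redacted parameter in that column should be left for the sponsor to check, because its schedule cannot be seen here.

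The cost is a change to one table column and one extra summary row. The downside is slightly fewer participants in the Week 12 row. No additional data collection is needed.

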15.6. Search Criteria for AESI

Table 15-2 Search Criteria for AESI

AESI	Search Criteria
Anaphylactic reactions	SMQ: Anaphylaxis [Narrow]
Systemic hypersensitivity reactions	SMQ: Hypersensitivity [Narrow]
Helminthic infections	HTLs of “Helminthic infections NEC”
Keratitis	PTs of 
 • Keratitis, Allergic keratitis • Ulcerative keratitis • Atopic keratoconjunctivitis • Herpes ophthalmic • Ophthalmic herpes simplex

Any severe type of conjunctivitis or blepharitis
	
1. Narrow conjunctivitis is defined as the following PTs
 
 • Conjunctivitis • Conjunctivitis allergic • Conjunctivitis bacterial • Conjunctivitis viral • Atopic Keratoconjunctivitis 
2. Broad conjunctivitis is defined as the following PTs
 
 • Conjunctivitis, Conjunctivitis allergic • Conjunctivitis bacterial • Conjunctivitis viral • Atopic Keratoconjunctivitis • Blepharitis • Dry eye • Eye irritation • Eye pruritus • Lacrimation increased • Eye discharge • Foreign body sensation in eyes • Photophobia, Xerophthalmia • Ocular hyperaemia • Conjunctival hyperaemia 
3. Conjunctivitis is defined as the following PTs
 
 • Conjunctivitis • Non-infective conjunctivitis • Conjunctivitis allergic • Conjunctivitis bacterial • Conjunctivitis viral • Eye irritation • Eye inflammation

Clinically symptomatic eosinophilia (or eosinophilia associated with clinical symptoms)
	
CMQ10641 based on HLT=Eosinophilic disorders or PT=Eosinophil count increased followed by blinded medical review for selection of relative events

Significant ALT elevation
	
- ALT $>5 \times$ the ULN in participants with baseline ALT $\leq 2 \times$ ULN or - ALT $>8 \times$ ULN if baseline ALT $>2 \times$ ULN

Pregnancy of a female participant entered in a study as well as pregnancy occurring in a female partner of a male participant entered in a study with IMP
	
“Pregnancy” or “Partner Pregnancy” checked in eCRF form “Pregnancy”

Symptomatic overdose (serious or nonserious) with IMP/NIMP	“Overdose of Study Treatment” or “Overdose of NIMP” checked and “Symptomatic overdose” checked in eCRF form “Overdose”
--	--

